**1. Is this project externally funded?  YES  NO**

If so, please list the funding source: Submitting for funding through Center for Biomedical Research Excellence (COBRE) in Cardiovascular Health Pilot Project

**2. Research Site(s)**

University of Delaware

Other (please list external study sites): Westside Family Health Center (various sites in New Castle County) and recruitment using Research Match.

Is UD the study lead?  YES  NO (If no, list the institution that is serving as the study lead)

### 4. Special Populations

Does this project involve any of the following:

Research on Children? No

Research with Prisoners? No

If yes, complete the Prisoners in Research Form and upload to IRBNet as supporting documentation

Research with Pregnant Women? No

Research with any other vulnerable population (e.g. cognitively impaired, economically disadvantaged, etc.)? please describe

Yes, participants will be recruited from Westside Family Health Center locations across New Castle County. Westside Family Health Center, is a Federally Qualified Health Center, which serves a racially, ethnically, linguistically, and socioeconomically diverse population.

### 5. RESEARCH ABSTRACT

Please provide a brief description in LAY language (understandable to an 8th grade student) of the aims of this project.

The objective of this study is to conduct a pilot study of a storytelling intervention for African Americans with hypertension. We will recruit 30 African Americans with hypertension to view six-eight patient stories and provide feedback on their effectiveness, usefulness, and satisfaction with the stories. [name] was awarded a Penn State Clinical and Translational Science Institute KL2 to develop a hypertension storytelling intervention, HBPStories. For the HBPStories project nine African Americans were filmed sharing their experiences living with and managing hypertension; including, diet and exercise tips, suggestions for locating healthy foods, and motivational stories about successfully controlling hypertension.

We will also elicit feedback from the participants about the best approaches for

delivering a storytelling intervention, and to obtain feedback on the resources and health information that would be helpful to an individual participating in a storytelling intervention.

**6. PROCEDURES** Describe all procedures involving human subjects for this protocol. Include copies of all surveys and research measures.

**Phase I:** We will recruit 30 African Americans with hypertension from Westside Family Health Center, which has multiple sites in New Castle County, using Google ads and Research Match. The participants will watch the stories and provide feedback on their engagement and satisfaction with the stories, the website, and recommendations for incorporating the stories into a future intervention. We will collect self-reported demographic data including age, gender/gender-identity, income, education, years since hypertension diagnosis, and participants will complete a health literacy screening using the Short-form Health Literacy Survey. The participants will watch the stories on the study website and complete a survey in REDCap. Participants will be asked to watch the eight patient videos (each 2-3 minutes in length) and complete a short 3-5-minute survey after each video. The same survey will be administered after each story (Table 1). We will use a Williams Latin Square to determine the order in which participants will watch the videos. This approach will be used to ensure that videos are not watched in the exact same order by the participants. After providing feedback on the individual stories, the participants will complete a 10-minute survey to gauge overall satisfaction with the stories, engagement, usefulness of the website, and potential uses for future studies. We will use the feedback from the survey to rank which stories were most informative and engaging and select the top six for phase II of the study. Participants will be invited to participate in a 30-minute exit interview to discuss their opinions on the stories, to discuss preferences for a hypertension study, how the stories could be used most effectively, and what type of study would be helpful for them and others managing hypertension. If participants report lack of engagement or satisfaction with the stories, we will ask for their feedback on how we might use the stories to be more helpful and what type of study design would be of interest to them. The study visit will take 1-1.5 hours to complete, and participants will receive a \$20 gift card upon completion of the surveys and an additional \$10 gift card for participating in the exit interview. The study visit will take place in person or via Zoom depending on the preference of the study participants. **Community Advisory Board:** We will invite Phase I participants to volunteer to participate in a community advisory board, we will meet with the community advisory board 2-3 times to request feedback on the findings of the first phase of the study, advice on how to incorporate the feedback from participants into the design of phase 2, and to provide suggestions for the design of Phase II of the study. We will meet with the community-advisory board at the close of the study and develop presentations to summarize the preliminary findings of the study and determine an approach for disseminating the findings of both phases of the study throughout the community. Community Advisory Board Meetings will be held in person and via Zoom. **Phase II:** Twenty participants will engage in a 6-week online storytelling intervention and provide feedback on the effectiveness, engagement, and recommendations for improving the intervention. Participants will complete a 10-item survey in REDCap after viewing the weekly story. The participants will also review the study website and access health materials from the American Heart Association covering topics such as using an electronic pill bottle to manage medication, working out at home, and cooking healthy meals. A list of the survey topics are listed in Table 1. Participants will be expected to spend 30-minutes to an hour each week viewing the stories and study material. Participants will complete a pre- and post-study survey to assess changes in diet, physical activity, and medication adherence during the study.

Participants will receive \$5 dollars for each week for a total of \$30 dollars and will receive a free blood pressure monitor. We will complete exit surveys with Phase 2 Study participants to ask about engagement, reasons for not participating/dropping out, satisfaction with the intervention, and approaches for improving the intervention.

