**15. Supporting Documentation**

Please list all additional documents uploaded to IRBNet in support of this application.

- Phase 1 Participant Survey (clean and edited version)
- Phase 2 Participant Survey (clean and edited version)
- e-Heals Health Literacy Questionnaire (clean and edited version)
- Consent Form Phase 1 (clean and edit version)
- Consent Form Phase 2 (clean and edited version)
- Cover letter to the IRB
- Recruitment Letter
- Letter of Support Westside Family Health Center
- Storytelling Feasibility Study Protocol (clean and edited version)

Rev. 10/2012

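### Does naming one health-literacy instrument in the procedures and another in the upload list put any result at risk?

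*Protocol*

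**What the plan says.** Section 6 (Procedures, Phase I) lists the participant characteristics to be collected: self-reported demographics, time since diagnosis, and a health-literacy measure. For the last of these it states that "participants will complete a health literacy screening using the Short-form Health Literacy Survey". No other health-literacy instrument is named there, and the Phase II description mentions no health-literacy measurement.

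The form prompt that opens Section 6 instructs the applicant: "Include copies of all surveys and research measures". Section 15 (Supporting Documentation) then asks: "Please list all additional documents uploaded to IRBNet in support of this application". The answer includes "Phase 1 Participant Survey (clean and edited version") and "e-Heals Health Literacy Questionnaire (clean and edited version"), along with the Phase 2 survey, the consent forms, letters and the protocol itself. The Short-form survey is not listed by name.

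**The concern.** Read together, the two sections look like a contradiction. The measure described in the procedures is missing by name from the upload list, and the measure on the list is missing from the procedures. A reader could fear that staff would give the uploaded questionnaire while the eventual paper follows Section 6 and reports the score under another instrument's name.

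The variable is a natural one to describe in this study. The intervention is video stories and a website, and Section 4 describes the population served by the recruiting health center as diverse in language and socioeconomic position. A mislabelled score would misdescribe the sample. Section 7 speaks of one study visit, so giving the wrong form could not be put right without contacting participants again. If the form were changed partway through, the scores might not be comparable across participants.

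**Working it through.** No sample size, error rate or effect size bears on this point, so there is nothing to compute. The check is a comparison of sections, followed by tracing where the variable is used.

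**Step 1: do the names match?** They do not. Section 6 names the Short-form Health Literacy Survey; Section 15 names the e-Heals questionnaire. Nothing in the visible text calls them the same instrument, says that one replaced the other, or says that both are given. The mismatch is in current text and does not come from a redaction or a broken table.

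**Step 2: does this establish a contradiction?** No.
- Section 15 gives file titles, not contents. Section 6 collects the screening in the same sentence as the demographic items, so its questions could well be inside the Phase 1 Participant Survey, which is on the list.
- Section 6 refers to Table 1 for survey content and survey topics, and that table is not in the text available. Part of the description of what is asked is therefore out of view.
- Section 6 does not say that the Short-form is the only health-literacy measure, and Section 15 does not tie e-Heals to a phase. Both could be in use.

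**Step 3: where does the variable enter?**
- *Eligibility (Section 7):* self-reported hypertension, prescribed antihypertensive medication, age, ability to consent, English, and plans to move. Health literacy is not among them.
- *Ranking and selection of the top six stories (Section 6, Phase I):* based on survey feedback about the stories. Health literacy plays no stated part.
- *Phase II comparison (Section 6):* diet, physical activity and medication adherence before and after. Health literacy plays no stated part.
- *Analysis and reporting (Section 10):* names the software and a mixed-methods paper. No analysis by health literacy is described.

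**Step 4: is there evidence of a change of form during the study?** None. The phrase about clean and edited versions is attached to most items in Section 15, including the consent forms and the protocol, so it describes the submission package and not a change during enrollment.

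**Step 5: what is the largest effect?** One descriptive variable, in at most the 30 Phase I participants, reported under the wrong name. That requires both that the form given is not the one named in Section 6 and that nobody notices when the paper is written.

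**The case for a change.** The strongest case for acting is that the choice of questionnaire belongs in the protocol, not in an analysis plan, and that the form itself asks for every measure to be supplied and every upload to be listed. Against those two instructions the document is inconsistent as it reads. Health literacy is also the only Phase I characteristic in Section 6 tied to a named instrument, so its meaning depends on knowing which one was used. One sentence would settle the matter, at no cost in participants, visits or budget.

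Much of this stands. The names differ, and the visible text leaves the reader to guess. What does not stand is the step from the names to a threatened result. The protocol nowhere says that health literacy will be used to interpret who found the stories engaging. Nor can the documents show that the two instruments measure different things or give scores that cannot be combined, because they describe neither the content nor the scoring of either one. That a correction is cheap does not show that any finding depends on it.

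**Conclusion.** The mismatch is real but clerical, and no change to the plan follows. It bears only on how one baseline descriptor is labeled, for at most 30 participants in a feedback pilot. Eligibility, the ranking of stories, the choice of six for Phase II and the Phase II pre- and post-study measures are untouched.

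This rests on two assumptions. The first is that health literacy has no role beyond describing the sample, which is all the visible text gives it. The second is that whoever reports the study names the instrument from the completed forms and not from the protocol narrative, which is ordinary practice. If an analysis plan or Table 1, neither of which is available here, made health literacy a stratifying or explanatory variable, the instrument's identity would matter more and the point would deserve another look. Otherwise, aligning the two names is housekeeping for the next routine submission.

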## **7. STUDY POPULATION AND RECRUITMENT**

Describe who and how many subjects will be invited to participate. Include age, gender and other pertinent information.

Study recruitment will be conducted at Westside Family Health Center sites in New Castle County, using Google ads and Research Match. Westside serves a racially, ethnically, and socioeconomically disadvantaged population of over 27,000 patients. Flyers and handouts will be provided to community organizations, social organizations, and shared at community events. In Phase 1 we will enroll 30 study participants, we anticipate 30-40 people will be screened to identify 30 that meet the inclusion and exclusion criteria. For Phase II we will recruit 30 participants, we anticipate screening 30-40 participants to identify participants that meet the inclusion and exclusion criteria. Westside Family Healthcare will be the primary recruiting site.

Attach all recruitment fliers, letters, or other recruitment materials to be used. If verbal recruitment will be used, please attach a script.

Not Applicable

Describe what exclusionary criteria, if any will be applied.

The study inclusion criteria are as follows: 1) self-reported hypertension; 2) prescribed antihypertensive medication; and 3) age  $\geq$  18 years. The exclusion criteria are: 1) cognitive limitations that limit the ability to provide informed consent; 2) unable to speak or read English and 3) are planning to move during the study period .

Describe what (if any) conditions will result in PI termination of subject participation.

Study subjects will participate in one study visit and will be asked to commit to spending 1-hour viewing the stories and providing feedback. If the participant is unable to spend an hour viewing the stories and providing feedback they will be withdrawn from the study. Participants that are withdrawn from the study will be replaced with new study participants.

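### Phase II is planned for 20 participants in Section 6 and 30 in Section 7, and the protocol does not reconcile the two

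*Protocol*

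**What the plan says.** The size of Phase II is given in two places in the protocol.

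- **Section 6 (Procedures), Phase II:** "Twenty participants will engage in a 6-week online storytelling intervention".
- **Section 7 (Study Population and Recruitment):** "For Phase II we will recruit 30 participants", followed by an expectation that 30 to 40 people will be screened.

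Phase I is consistent by comparison. Section 6 says "We will recruit 30 African Americans with hypertension from Westside Family Health Center" and Section 7 says "In Phase 1 we will enroll 30 study participants".

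Two other passages bear on the number.

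- **Withdrawal and replacement (Section 7):** the paragraph on ending participation opens with "Study subjects will participate in one study visit", sets a one-hour commitment, and ends with "Participants that are withdrawn from the study will be replaced with new study participants". It names no phase.
- **Payment (Section 6):** each Phase II participant is paid $5 a week, $30 in all, and "will receive a free blood pressure monitor".

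**The concern.** Both sentences describe how many people Phase II will include, and they give different numbers. Section 7 answers the form's question about how many subjects there will be; Section 6 is the description of procedures that staff will follow. Enrolling participants 21 to 30 would comply with Section 7 and exceed Section 6. Stopping at 20 would meet Section 6 and fall short of Section 7.

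In a feasibility pilot, whether recruitment reached its target is a natural thing to report. With two targets that statement has no fixed meaning. The per-participant costs are uncertain for the same reason.

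The point is not that a sample-size justification is missing. The protocol states the planned number twice, with different values.

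**Working it through.** **Inputs**

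| Quantity | Value | Source in protocol |
|---|---|---|
| Phase II size | 20 | Section 6, Phase II |
| Phase II size | 30 | Section 7 |
| Phase II screened | 30 to 40 | Section 7 |
| Phase I size | 30 and 30 | Sections 6 and 7 |
| Phase II payment | $5 a week for 6 weeks | Section 6 (the $30 maximum is also in Section 9) |
| Phase II dropout rate | none given | – |

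The protocol gives no formula, power, effect size or dropout rate, so neither 20 nor 30 can be derived. What can be tested is whether anything in the text turns one into the other.

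**Size of the gap.** 30 − 20 = 10, which is 10/30 = 33% of the larger figure and 10/20 = 50% of the smaller. Rounding cannot account for it.

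**Could screening explain it?** No. The screening range of 30 to 40 is given in addition to the 30 recruited.

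**Could dropout explain it?** If 20 were the number to be retained and d the proportion lost, the number to recruit is 20/(1 − d), rounded up. Under assumed values of d:

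| Assumed d | 20/(1 − d) | Recruit |
|---|---|---|
| 10% | 22.2 | 23 |
| 20% | 25.0 | 25 |
| 25% | 26.7 | 27 |
| 30% | 28.6 | 29 |
| 33.3% | 30.0 | 30 |

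Reaching 30 needs d = 1 − 20/30 = 33.3%. The protocol states no such rate and no completer target.

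**Could the choice of verb explain it?** Phase I offers a check. The same 30 people are recruited in Section 6 and enrolled in Section 7, so the document does not consistently use recruitment for a larger group than enrolment.

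**Could the replacement rule explain it?** It follows a one-visit, one-hour condition, which does not describe a six-week intervention. If it did apply to Phase II, it would hold the number constant rather than let it fall from 30 to 20.

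**Does the abstract settle it?** Section 5 speaks of 30 people viewing six to eight stories and giving feedback. It names no phase, and the description fits Phase I.

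**What scales with the number**

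- Target met if 20 enrol: 20/20 = 100%, or 20/30 = 67%.
- Gift cards: $5 × 6 = $30 each; 20 × $30 = $600, or 30 × $30 = $900, a difference of $300.
- Blood pressure monitors: 20 or 30, a difference of 10.
- Precision, for illustration only, since the protocol sets no precision goal. The 95% confidence interval half-width for a proportion of 0.5, 1.96 × √(0.25/n), is 22 percentage points at n = 20 and 18 at n = 30. For a mean pre-post change, t(0.975, n − 1)/√n gives 0.47 and 0.37 standard deviations of the change.

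**The case against.** The best defence is that the two sentences count different things: 30 are recruited and 20 go on to take part. There is some support for it. Section 6 plans Phase II exit surveys that ask why people did not take part or dropped out, so some loss is foreseen. In Section 7 the Phase I sentence speaks of enrolling and says 30 eligible people will be identified, while the Phase II sentence speaks of recruiting and does not repeat a number of eligible people. On that reading the missing 10 could be ineligible, never started or dropped out, so calling the whole gap attrition would assume too much.

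This keeps the reading open but does not establish it. Foreseeing dropout as a survey topic supplies neither a rate nor a target, and the change of verb is equally consistent with loose drafting. The caution about attrition does stand: if the sponsor means two different quantities, the text should say what each one is.

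It can also be said that the matter is small: an uncontrolled, minimal-risk pilot with no power claim, $300 in gift cards and 10 monitors. That is a fair account of the consequences, and it limits the weight of the point. It does not make two different planned sizes acceptable in the document that fixes enrolment.

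**Conclusion.** The planned size of Phase II is stated inconsistently, 20 in Section 6 and 30 in Section 7, and the protocol contains nothing that reconciles them. The discrepancy is 10 participants, 33% of the larger figure. It should be corrected, but its reach is modest: it makes the recruitment target ambiguous and leaves the gift-card total ($600 or $900) and the number of monitors (20 or 30) undetermined. No hypothesis test, precision goal or retention criterion stated in the protocol depends on it.

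The cost figures assume that every participant completes all six weeks. The document does not show which number is intended, and this review does not choose between them.

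**What to change.** State one Phase II enrolment number and use it in both Section 6 and Section 7. If the two figures are meant as different quantities, label each one (for example, 30 enrolled and 20 expected to complete) and state the expected loss of 10 of 30 (33%), saying whether it falls before or after the intervention starts. It would help, as a side point, to say whether the Section 7 replacement rule covers Phase II.

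The cost is a short wording amendment to two sections, plus a check of any other study document that repeats the number, such as the item listed in Section 15 as "Consent Form Phase 2 (clean and edited version", which is not among the material reviewed. No procedure or outcome changes.

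### Does Phase II need changing because its pre/post outcomes overlap the health materials and a blood pressure monitor given alongside the stories?

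*Protocol*

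**What the plan says.** Section 6 (Procedures) of the protocol describes Phase II as one group with no comparator: "Twenty participants will engage in a 6-week online storytelling intervention and provide feedback on the effectiveness, engagement, and recommendations for improving the intervention". Section 7 gives a different size: "For Phase II we will recruit 30 participants".

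Besides the weekly story, participants look through the study website and use American Heart Association materials "covering topics such as using an electronic pill bottle to manage medication, working out at home, and cooking healthy meals". Weekly exposure is stated for everything together: "Participants will be expected to spend 30-minutes to an hour each week viewing the stories and study material".

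Behaviour is measured before and after: "Participants will complete a pre- and post-study survey to assess changes in diet, physical activity, and medication adherence during the study".

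The closing lines on Phase II in Section 6 describe a payment of \$5 a week and say that participants "will receive a free blood pressure monitor". No hand-out date is given. Section 9 (Compensation) covers gift cards and does not mention the monitor.

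Section 5 (Research Abstract) calls the study a pilot. It says the filmed stories themselves contain advice on eating and exercise. It also lists, as something to learn, which resources and health information would help people taking part in a storytelling intervention.

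**The concern.** The three surveyed outcomes are diet, physical activity and medication adherence. The three example topics of the health materials are healthy cooking, home workouts and an electronic pill bottle. Each outcome has a matching topic in a component that is not a story. A home monitor, if handed out early, might also prompt people to attend to their medication. All of this runs at once in one uncontrolled group under the name of a storytelling intervention.

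If behaviour improved, a reader might credit the stories when the materials, the monitor, the passage of time or repeated questioning could have done the work. A later trial might then rest on an effect that belongs to something else.

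**Working it through.** The protocol states no effect size, SD, power or confidence level for Phase II, so there is no planned figure to reproduce. Four checks apply.

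**1. What the design can estimate.** Inputs: one group; one survey before and one after; stories, materials and (on the worst assumption about timing) the monitor all starting in between. With columns for intercept, time, stories, materials and monitor, the two kinds of row are:

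- before: (1, 0, 0, 0, 0)
- after: (1, 1, 1, 1, 1)

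The matrix has rank 2 and 5 columns. Only a baseline level and one total change can be estimated. If the monitor is held back until after the final survey, its column drops out and the rows become (1, 0, 0, 0) and (1, 1, 1, 1): rank 2 with 4 columns. Stories, materials and time are still inseparable. The number of participants does not enter.

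**2. Precision of that total change.** Half-width of the 95% interval, in SDs of the individual change, is t(0.975, n−1)/√n:

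- n = 20: 2.093/4.472 = 0.468 SD
- n = 30: 2.045/5.477 = 0.373 SD

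These figures describe sampling error in the package-level change. They say nothing about confounding. An assumed contribution of 0.2 to 0.4 SD from materials and monitor could not be told apart from a story effect of the same size, but by check 1 that would hold at any sample size.

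**3. What the text claims, set against what the design supports.**

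- The survey is there to assess changes during the study. The sentence names no cause.
- Effectiveness appears as something on which participants "provide feedback on the effectiveness, engagement, and recommendations for improving the intervention". That is perceived effectiveness, gathered with engagement and suggestions.
- Stories and materials share one weekly time allowance, and Section 5 treats feedback on helpful resources as part of the purpose. The materials are part of what is being piloted.
- The overlap is not exclusive to the materials. By Section 5 the stories also cover diet and exercise, so at least two of the three outcomes are story topics too. The topics quoted for the materials are only examples.
- Whether use of the materials is recorded cannot be judged. Section 6 refers to Table 1 for survey topics, and Section 15 lists the Phase 2 Participant Survey as a separate upload; neither is in the text at hand.

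**4. What a comparator would buy.** This is an illustration with assumptions outside the protocol: 1:1 allocation to stories plus materials or materials alone, two-sided 5% level, 80% power, normal approximation, no dropout. The detectable difference is (1.960 + 0.842) × √(2/n per arm):

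- 10 per arm: 2.802 × 0.447 = 1.25 SD; power for 0.5 SD is about 20%
- 15 per arm: 2.802 × 0.365 = 1.02 SD; power for 0.5 SD is about 28%

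At this size a control group would not settle the question.

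**The case for a change.** The best case for acting is that this goes beyond the usual remark that single-arm pilots are uncontrolled. Section 6 puts each video at 2 to 3 minutes in Phase I. If Phase II uses one such video a week within a 30 to 60 minute allowance, a single viewing takes between 2/60 = 3% and 3/30 = 10% of the expected time. Most of the exposure could then be website and materials, which makes the storytelling label a weak guide to what caused any change. The results are to be published and shared with the community, and nothing in the protocol limits how they are read. The remedies are cheap: a sentence on when the monitor is given, a survey item on materials opened, and a sentence saying that change belongs to the whole package. The first two cannot be added once the data are in.

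The first part stands: the change belongs to the package, and a report should say so. The remedies carry less weight. Dating the monitor fills in an unstated detail and, by check 1, leaves stories, materials and time aliased. A survey item on materials may duplicate one that already exists, and because participants choose what to open, it would not isolate the stories. The interpretive sentence corrects no rule, figure or conclusion, because the protocol draws no conclusion of that kind. Choosing a mean change with an interval is the sort of detail a protocol commonly leaves to the analysis plan.

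**Conclusion.** The limitation is real and complete: in Phase II the effect of the stories cannot be separated from the materials or from time, whether 20 or 30 people take part. It is a fair trade-off for a small pilot and not an error, because the protocol measures change without attributing it and asks for opinions on effectiveness. An analyst who reports pre/post change for the package as delivered, with an interval of roughly ±0.37 to ±0.47 SD, stays within what the design supports.

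The monitor is the weakest part of the concern. Its timing is unknown, it matters only if given before the final survey, and blood pressure is not among the listed pre/post outcomes. That materials use goes unrecorded cannot be shown from the text at hand.

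The conclusion assumes that the reports keep to the protocol's descriptive wording. A report that credited change to the stories alone would be wrong, but the fault would lie in the report. The authors may choose to state when the monitor is handed out and which materials were used; neither would isolate the story effect. The differing Phase II sizes in Sections 6 and 7 are a separate matter and do not affect this point.
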